4.4.2 Safety Variables

Safety will be evaluated by monitoring AEs and SAEs, results of ophthalmic examinations (including slit-lamp biomicroscopy and dilated fundus parameters, as well as measurements of BCVA and intraocular pressure [IOP]).

All AEs will be captured whether or not considered to be related to the surgical procedure, implant, or CNTF. The incidence of reported AEs will be compared between the treated and sham participants, particularly with respect to ocular AEs. An attempt will be made to differentiate between treatment-

related AEs and AEs considered to be part of the normal progression of the disease. In addition, for treatment-related AEs, an attempt will be made to differentiate those that the investigator believes are due to the device itself, to CNTF, or to the implant/sham procedure.

5 SAMPLE SIZE CONSIDERATIONS

Sample size calculation is based on the comparison of the 2 groups over 24 months (720 days) incorporating a longitudinal mixed effects model. The number of participants, N, in each of the 2 groups [15] is calculated as follows: We assume that, in the NT-501 implant group, the response of change in EZ area is as follows:

$$Y_{ij} = \beta_{0NT-501} + \beta_{1NT-501}x_{ij} + \varepsilon_{ij}, \quad j = 1, \dots, n; i = 1, \dots, m$$

For the sham group the sham equation holds as follows:

$$Y_{ij} = \beta_{0sham} + \beta_{1sham}x_{ij} + \varepsilon_{ij}, \quad j = 1, \dots, n; i = 1, \dots, m$$

Both groups have the same number of participants (m), $x_{ij} = x_j$ represents the duration between the first and the jth visit in which case β_{1sham} and $\beta_{1NT-501}$ represents the rates of change in Y for Sham and NT-501 implant, respectively, and each person is measured at the same time points, and each participant has n repeated observations of EZ area planned to occur at baseline, 12, 16, 20 and 24 months (where months will be converted to years).

The number of participants, m, in each of the 2 groups [15] is calculated as follows:

$$m = \frac{2(z_{\alpha} + z_{\beta})^2 \sigma^2 (1 - \rho)}{ns_x^2 d^2}$$

where $d = \beta_{1sham} - \beta_{1NT-501}$ and s_x^2 is the within-subject variance of x_j .

Using the above equation with a Type 1 error rate of 0.05 (2-sided); variance of endpoint (σ^2)= 0.0256; correlation between within participant observations (ρ) = 0.6; $s_x^2 = 0.47$ and n = 5 (baseline and 12, 16, 20 and 24 months) we have 80% power with a sample size of 50 participants per treatment group to detect a difference in rate of change 0.037 mm²/year in the EZ area in the NT-501 implant group versus the sham group. The sample size will be increased to 56 participants per treatment group (112 total participants) to provide adequate power in the analysis of the population evaluable for efficacy.

The statistical model will be a random intercept model as follows:

$$Y_{ij} = (\beta_0 + b_{0i}) + \beta_1 * TRT + \beta_2 * TIME + \beta_3 * TRT * TIME + \varepsilon_{ij}$$

where Y_{ij} is the efficacy endpoint (EZ area) measurement for participant $i = 1, 2, \dots, n$ at time point $j = 1, \dots, K$. TRT is an indicator of the participant i 's treatment group (i.e., TRT = 1 for NT-501 implant; TRT = 0 for sham) and TIME is the annualized time. To compare the rate of change from baseline in EZ area between the 2 treatment groups the primary hypothesis is as follows:

$$H_0: \beta_3 = 0 \text{ versus } H_1: \beta_3 \neq 0$$

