Safety data from approximately 250 participants implanted with the NT-501 device (nominal dose 20 ng/24 hours) suggest that adverse events (AEs) are generally limited to those related to the implant procedure. A number of participants have reported miosis, which is believed to be directly related to CNTF. During early development, a number of participants developed inflammation following implantation. This was subsequently related to impurities in the membrane. Trace to mild inflammation is seen postoperatively in a minority of participants and typically clears by 3 months. In the Phase 2 study, one episode of delayed inflammation (grade 3) was noted at 6 months and resolved by 12 months.

Studies of NT-501 in RP and AMD did not demonstrate any potential benefit. However, in the NTMT-02 study of 67 participants (99 eyes randomized 1:1) with MacTel, there was a statistically significant reduction in the rate of progression of MacTel in the eyes implanted with NT-501 as compared with the eyes that underwent the sham procedure. The mean (standard error [SE]) area of EZ break increased by 0.218 (0.049) mm² in the implanted eyes and by 0.270 (0.050) mm² in the sham eyes. The difference between groups in the increase of the MacTel lesion (0.052 mm²) was statistically significant ($p = 0.039$, 1-sided). The mean change in retinal sensitivity as measured by microperimetry was not different between the treated and sham eyes. However, when the aggregate retinal sensitivity (dB) was compared with the corresponding area affected by MacTel, a difference between treated and sham eyes was detected. This difference was consistent with the slower growth of the MacTel lesion in the treated eyes. There was a significant difference between treatment groups in reading speed at 24 months (13.5 words read per minute, $p = 0.016$). Specifically, the implanted eyes had not deteriorated from baseline (0.03 words read per minute), but the sham eyes showed impairment in reading speed relative to baseline (-13.5 words read per minute). The mean (SE) macular thickness was significantly increased in the treated population when compared with the sham group (NT-501: +5.45 [3.02] μ ; sham: -4.97 [2.85] μ ; $p = 0.007$). The mean (SE) pupil size was also significantly reduced in the implanted eyes as compared with the sham eyes (difference between groups: 0.922 [0.13] mm, $p < 0.0001$).

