As of September 2019, a total of 64 participants (94 study eyes) were consented in the Phase 2 Extension Study, and of those, 92 study eyes had EZ break grading at 36 months and 86 had EZ break grading at 48 months. The mean (standard error [SE]) area of EZ break at 36 months was 0.149 (0.035) mm² in the implanted eyes and 0.241 (0.032) mm² in the sham eyes. The difference between groups in the increase of the MacTel lesion (0.092 mm²) was statistically significant ($p = 0.022$, 1-sided). The mean (standard error [SE]) area of EZ break at 48 months was 0.211 (0.059) mm² in the implanted eyes and 0.208 (0.056) mm² in the sham eyes. The difference between groups in the increase of the MacTel lesion (0.077 mm²) did not meet statistical significance ($p = 0.488$, 1-sided). There was not a statistically significant difference between treatment groups in reading speed at 36 months (10.6 words read per minute, $p = 0.093$), or 48 months (5.4 words read per minute, $p = 0.202$). The mean (SE) pupil size for all NTMT-02 Extension Study participants was reduced in the implanted eyes as compared with the sham eyes at 36 months (difference between groups: 0.805 [0.14] mm, $p < 0.0001$) and 48 months (difference between groups: 0.844 [0.15] mm, $p < 0.0001$).

Consistent with the experience of the NT-501 device in studies of RP and dry AMD, the device was generally well tolerated in the Phase 2 study. No participant had the implant removed during the course of the study. The AEs considered related to the device could be grouped into those resulting from the procedure and those related to the parasympathetic agonistic effect of CNTF. One participant (2 eyes) reported an ophthalmic serious adverse event (SAE) of an extended hospital stay (1 day) because of blurred vision immediately following the procedure. This event resolved without sequelae.

In the current study, participants with a confirmed diagnosis of MacTel and an EZ break area of at least 0.16 mm² and no greater than 2.00 mm² will be randomly assigned to 1 of 2 treatment groups: implantation of the NT-501 device or sham surgery with no implant. A single device will be inserted into the study eye for the 24 to 48-month duration of the study.

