7.2.2 Visit 0: Randomization and Surgery

If the participant meets all study criteria, including those determined by the reading center, and continues to agree to participate in the study, then the implant surgery/sham procedure date may be confirmed. **The implant surgery/sham procedure in the study eye should be completed within 30 days of randomization and/or up to 58 days from screening.** The study's electronic data capture (EDC) system will assign the randomization assignment. The participant study eye will be randomized using the EDC system prior to the implant surgery/sham procedure. The study eye will be randomized (1:1) to receive the NT-501 implant or to undergo the sham procedure. Only 1 eye per participant will be randomized. If both eyes qualify for the study, the study eye will be selected using the centralized randomization process.

On the date of the surgery, the investigator will confirm that no change in the participant's general condition has occurred that would exclude study participation.

The following evaluations/procedures will be conducted during this visit:

- If not already completed: medical evaluation, standard for any surgical procedure or anesthesia (the specific tests to be ordered will be site-specific)
- Any further medical/ophthalmic history
- Any additional concomitant medications
- AE assessment (from the time surgery begins)
- BCVA (may be performed within 1 week prior to the day of surgery)

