12.2 SAMPLE SIZE

Sample size calculation is based on the comparison of the 2 groups over 24 months incorporating a longitudinal mixed effects model. The number of participants, N, in each of the 2 groups²² is calculated as follows: We assume that, in the NT-501 group, the response of change in EZ area is as follows:

$$Y_{ij} = \beta_{0 NT-501} + \beta_{1 NT-501}x_{ij} + \varepsilon_{ij}, \quad j = 1, \dots, n; i = 1, \dots, m$$

For the sham group the sham equation holds as follows:

$$Y_{ij} = \beta_{0 Sham} + \beta_{1 Sham}x_{ij} + \varepsilon_{ij}, \quad j = 1, \dots, n; i = 1, \dots, m$$

Both groups have the same number of participants (m), $x_{ij} = x_j$ represents the duration between the first and the jth visit in which case $\beta_{1 Sham}$ and $\beta_{1 NT-501}$ represents the rates of change in Y for Sham and NT-501, respectively, and each person is measured at the same time points, and each participant has n repeated observations of EZ area at baseline, 12, 16, 20 and 24 months (where months will be converted to years).

The number of participants, m, in each of the 2 groups²² is calculated as follows:

$$m = \frac{2(z_{\alpha} + z_{\beta})^2 \sigma^2 (1 - \rho)}{ns_x^2 d^2}$$

where $d = \beta_{1 Sham} - \beta_{1 NT-501}$ and s_x^2 is the within-subject variance of x_j .

Using the above equation with a Type 1 error rate of 0.05 (2-sided); $\sigma^2 = 0.0256$; $\rho = 0.6$; $s_x^2 = 0.47$ and $n = 5$ (baseline and 12, 16, 20 and 24 months) we have 80% power with a sample size of 50 participants per treatment group to detect a difference in rate of change 0.037 mm²/year in the EZ area in the NT-501 group versus the sham group. The sample size will be increased to 56 participants per treatment group (112 total participants) to provide adequate power in the analysis of the population evaluable for efficacy.

The statistical model will be a random intercept model as follows:

$$Y_{ij} = (\beta_0 + b_0) + \beta_1 * TRT + \beta_2 * TIME + \beta_3 * TRT * TIME + \varepsilon_{ij}$$

where Y_{ij} is the efficacy endpoint (EZ area) measurement for participant $i = 1, 2, \dots, n$ at time point $j = 1, \dots, K$. TRT is an indicator of the participant i 's treatment group (ie, TRT = 1 for NT-501; TRT = 0 for sham) and TIME is the annualized time. To compare the rate of change from baseline in EZ area between the 2 treatment groups the primary hypothesis is as follows:

$$H_0: \beta_3 = 0 \text{ versus } H_1: \beta_3 \neq 0$$

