5.1.1 Rationale for Parameters Used in Power Estimation

The NTMT-02 (Phase 2) allowed for the inclusion of both eyes in the study. If both eyes were eligible the right eye was randomized (1:1) to receive the NT-501 implant or sham procedure and the left eye received the alternative (surgery/sham). The sample size calculated above was based on estimates from an analysis incorporating NTMT-02 study design. Assuming independence between eyes the variance estimate (σ^2) is higher, yet the ρ is much higher with an estimate of power slightly higher 80%. Given the design of the NTMT-03A we assume similar estimates as those found in analysis assuming independence between eyes.

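### Is the 80% power claim unsupported because its variance inputs come from a two-eye Phase 2 study?

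*SAP*

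**What the plan says.** SAP 5 and Protocol 12.2 give the same calculation: a slope-comparison formula with five EZ area measurements (baseline and Months 12, 16, 20 and 24), two-sided alpha of 0.05, σ² = 0.0256, ρ = 0.6 and s_x² = 0.47. The SAP concludes that "we have 80% power with a sample size of 50 participants per treatment group to detect a difference in rate of change 0.037 mm²/year". Both documents then raise the number to 56 per arm so that the evaluable population keeps adequate power.

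SAP 5.1.1 explains the inputs: "The sample size calculated above was based on estimates from an analysis incorporating NTMT-02 study design". Phase 2 could enrol both eyes, with the second eye receiving the alternative assignment. For an analysis treating eyes as independent, it says that the variance is higher, "yet the ρ is much higher with an estimate of power slightly higher 80" per cent. It closes with: "Given the design of the NTMT-03A we assume similar estimates as those found in analysis assuming independence between eyes". Protocol 7.2.2 confirms the one-eye design: "Only 1 eye per participant will be randomized".

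The only other variance information is in Protocol 1.1. At 24 months in Phase 2 (99 eyes of 67 participants), the area "increased by 0.218 (0.049) mm² in the implanted eyes and by 0.270 (0.050) mm² in the sham eyes", a difference of 0.052 mm² with one-sided p = 0.039. At 36 months (92 eyes) the figures are "0.149 (0.035) mm² in the implanted eyes and 0.241 (0.032) mm² in the sham eyes", a difference of 0.092 mm² with one-sided p = 0.022.

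**The concern.** A design with two eyes in one participant can remove between-participant variation that a one-eye trial has to carry. If σ² and ρ came from the former, the 80% might not transfer to the latter. The analysis that would settle this is described only in words. The formula also has no term for participants progressing at different rates, and at 50 per arm it leaves almost no room for one. If the Phase 2 arm standard errors are taken as independent standard errors of change, power falls well below 80%. The target of 0.037 mm²/year also exceeds both Phase 2 differences (0.052/2 = 0.026 and 0.092/3 = 0.031 mm²/year). At stake is the stated justification for 112 participants, and how a null result would be read.

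**Working it through.** **The plan's own figure.** σ²(1−ρ) = 0.0256 × 0.4 = 0.01024, and n·s_x² = 5 × 0.47 = 2.35. The schedule 0, 1, 1.333, 1.667, 2 years gives s_x² = 0.471, which agrees with the printed value.

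m = 2(1.960 + 0.8416)² × 0.01024 / (2.35 × 0.037²) = 49.97, so 50 per arm. Power = Φ(0.037/√(2 × 0.01024/(2.35m)) − 1.96), which is 80% at m = 50 and 84% at m = 56. The arithmetic is right.

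**The SD that the plan implies.** For a change between two visits, SD = √(2 × 0.01024) = 0.143 mm².

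**24-month p-value.** One-sided p = 0.039 corresponds to z = 1.762, so the SE of the difference is 0.052/1.762 = 0.0295. Treated as unpaired with 49 and 50 eyes, SD = 0.0295/√(1/49 + 1/50) = 0.147, close to the plan's 0.143. Putting 0.147²/2 = 0.0108 in place of 0.01024 gives about 78% at 50 per arm and 82% at 56.

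**24-month arm SEs, read as unpaired.** The SE of the difference would be √(0.049² + 0.050²) = 0.070, so z = 0.052/0.070 = 0.74 and one-sided p = 0.23, against 0.039 printed. This reading does not fit the reported test. Pairing would have to be very strong to explain the gap. There were 99 − 67 = 32 bilateral and 35 unilateral participants, and the implied per-eye variance is 49.5 × (0.049² + 0.050²)/2 = 0.1213. With a between-eye correlation of 0.88, the paired part has variance 2 × 0.1213 × 0.12/32 = 0.00091 and the unpaired part 2 × 0.1213/17.5 = 0.01386. Combined optimally, the SE is 0.029. So a correlation near 0.88 would be needed.

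**36-month arm SEs, read as unpaired with 46 eyes per arm.** z = 0.092/√(0.035² + 0.032²) = 1.94 and p = 0.026, near the printed 0.022. Variance of change = 46 × (0.035² + 0.032²)/2 = 0.0517 (SD 0.227). Keeping the plan's residual and assigning the rest to slope gives τ² = (0.0517 − 0.0205)/9 = 0.00347, a slope SD of 0.059 mm²/year. Power = Φ(0.037/√((2/m)(0.01024/2.35 + 0.00347)) − 1.96), which is 55% at 50 and 60% at 56. Other splits of that variance give 42% to 68% at 50 and 46% to 73% at 56.

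**Do the two SE rows agree?** The same split at 24 months gives τ² = (0.1213 − 0.0205)/4 = 0.0252, a slope SD of 0.159. That predicts a 36-month arm SE of √((0.0205 + 9 × 0.0252)/46) = 0.073. The protocol prints 0.035 and 0.032. Under a slope-variance model the SD of change should grow with time, but here it falls from 0.348 to 0.227. The rows cannot both be independent SEs of change from one such process.

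**Room for slope variance at 56 per arm.** 80% power needs an SE of at most 0.037/2.8016 = 0.01321, so a per-participant slope variance of at most 56 × 0.01321²/2 = 0.00488. Subtracting 0.01024/2.35 = 0.00436 leaves about 0.0005, a slope SD of 0.023 mm²/year. At 50 per arm there is practically none, because 49.97 was rounded to 50.

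**Smaller effects on the plan's own variance.** At 0.026 mm²/year power is 50% (50 per arm) and 55% (56 per arm). At 0.031 it is 64% and 69%.

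**The case for a change.** The strongest case for acting is this. SAP 5.1.1 takes its printed numbers from one analysis and its assumption for this trial from another, and the second has no numbers. Protocol 12.1 says that the SAP will hold the sample size justification. The 24-month p-value, which supports the plan, may benefit from paired eyes that this trial lacks. The 36-month row is the one place where the unpaired reading roughly matches its p-value, and no split of its variance reaches 80%. The effect-size point needs no assumption about pairing at all.

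What stands is that the independent-eye σ² and ρ, any slope variance, and the origin of 0.037 are not printed.

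The inference to low power does not stand. The 36-month evidence is weak: both means (0.149 and 0.241) are below the 24-month increases (0.218 and 0.270) in a progressive disease, and the text calls them areas of break, not changes. The adjoining 48-month row contradicts itself (means 0.003 apart, stated difference 0.077). The 55% and 60% also describe a test that carries slope variance in its SE, while the planned model has a random intercept only. Whether that model should have a random slope is a separate question that sample size wording cannot settle. Finally, a design difference need not equal the Phase 2 estimate, so power at 0.026 is useful context, not a correction.

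**Conclusion.** No change follows. The stated power is arithmetically correct: 80% at 50 and 84% at 56 per arm. SAP 5.1.1 recognises the move to a one-eye design and reports that the independent-eye analysis gave slightly more than 80%. A higher σ² with a much higher ρ is coherent with that, because the formula depends only on σ²(1−ρ), which needs to be no more than about 0.0102.

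The Phase 2 figures do not settle the matter. They give about 78% and 82% from the 24-month p-value, and about 55% and 60% from the 36-month standard errors. These rest on assumed near-equal arms, an unpaired reading, and, for the second pair, the chosen variance split. True power may be below 80%, but the documents do not establish it.

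What remains is missing detail. Supplying it would leave enrolment, model, alpha and the trial's result as they are. SAP 4.1 expects the last participant to finish 24 months in about August 2022, so recruitment would have closed about two years before that, ahead of the current protocol version of 31 August 2021. A null result would be read from the 95% confidence interval for the treatment-by-time term that SAP 9.1 already requires, which reflects the variance observed and not the planning value.

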5.1.1 Rationale for Parameters Used in Power Estimation

The NTMT-02 (Phase 2) allowed for the inclusion of both eyes in the study. If both eyes were eligible the right eye was randomized (1:1) to receive the NT-501 implant or sham procedure and the left eye received the alternative (surgery/sham). The sample size calculated above was based on estimates from an analysis incorporating NTMT-02 study design. Assuming independence between eyes the variance estimate (σ^2) is higher, yet the ρ is much higher with an estimate of power slightly higher 80%. Given the design of the NTMT-03A we assume similar estimates as those found in analysis assuming independence between eyes.

6 SUMMARY OF MODIFICATIONS

6.1 Modifications from the Approved Statistical Analysis Plan

This is the fourth version of the SAP for the Final Analysis. The major changes to this version include changes to the description of the secondary endpoints because of the addition of two study visits, Month 36 and Month 48, with amendment 5 of the study protocol. An additional change was made to the criteria for including in the per protocol analysis. This change has been added because of the marked increase in missed and out-of-window visits due to the COVID-19 pandemic.

7 GENERAL STATISTICAL CONSIDERATIONS

7.1 General Principles

All continuous variables at baseline and in terms of changes from baseline will be summarized using the following descriptive statistics: N (total number of participants in the population), n (total number of participants in the population with a given condition), mean, standard deviation (SD), median, maximum and minimum. Precision of the measurement for each continuous variable will be used to determine the number of decimal places to present in tables, figures, and derived listings. If the measurements in the source (raw) data are integers, the corresponding mean and median will be presented in 1 decimal place and the SD in 2 decimal places; if the measurements are in 1 decimal place, the mean and median will be in 2 decimal places and the SD in 3 decimal places; and so forth. Minimum and maximum will be displayed as reported in the source (raw) data. Any values that require transformation to standard units (metric or SI) will be converted with the appropriate corresponding precision. The frequency and proportion of observed levels will be reported for all categorical measures. Categorical variables will be summarized using counts and percentages. Percentages will be presented to 1 decimal place unless otherwise specified in the statistical programming document for the study.

When appropriate, corresponding exact 95% confidence intervals will be included. In general, all data will be listed, sorted by site, treatment group and participant, and by visit number within participants when appropriate. All summary tables will be structured with a column or row for each treatment group. Descriptive summaries of study endpoints across each visit will be presented in tables by treatment group. Inferential summaries of study endpoints in which formal statistical testing is implemented will be performed and presented by treatment group. Descriptive graphical summaries of study endpoints will be presented by treatment group and visit. In general, all data will be listed, sorted by site, treatment and participant, and when appropriate by visit number within participant.

The baseline value will be defined as the most recent non-missing measurement collected during a screening visit. For example, if a participant was re-screened for the study, the baseline value will be the 2nd screening value. The change from baseline value will be defined as post-baseline value minus baseline

value. These definitions will apply to all analysis variables: demographics, background, baseline characteristics, efficacy and safety, unless otherwise specified.

Unscheduled measurements will be recorded as such and not attributed to a scheduled measurement time point, unless otherwise specified. Where applicable, visit windows for efficacy analysis are presented in the relevant section.

Incomplete/Missing data: Missing post-baseline values will not be imputed for the primary efficacy analysis conducted using longitudinal mixed effects methods, which make use of all available data even if a participant has missing data at some post-baseline visits. For some endpoints, sensitivity analysis including imputation may be conducted. Where applicable, these analyses have been indicated in Section 9.1.1.

For safety analysis, no imputation will be used. Missing data (e.g., dates) will remain as missing, and conservative conventions established, as required. These will be documented in the statistical programming document for this study.

No formal statistical analyses will be performed to detect and/or remedy the presence of statistical outliers.

Measurements recorded more than once at a certain time point are defined as replicate observations. If a measurement is replicated and both are valid, the first recorded measurement will be used for analysis. Replicated measurements are expected for the baseline MAIA.

Measurements recorded for the same participant at different time points are defined as repeated observations. If an assessment has planned repeated measurements, then statistical summaries will present all planned time points, as appropriate (e.g., EZ area loss).

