7.2.5 Visit 3: 1 Month Postsurgery (± 7 Days)

In France only, the following evaluations/procedures will be conducted during this visit:

- AE assessment

- Review concomitant medications
- Manifest refraction, only required if there is deterioration of 10 or more letters from baseline
- BCVA
- Goldmann applanation tonometry (study eye only)
- Measurement of undilated pupil diameter (study eye only)
- Slit-lamp biomicroscopy (study eye only)
- Dilated fundus examination (study eye only)
- Implant/sham site examination (study eye only)

In regions other than France, telephone contact will be made with the participant to determine the following:

- AE assessment
- Review concomitant medications

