18. STUDY DISCONTINUATION

Both the sponsor and the principal investigator reserve the right to terminate the study at the investigator's site at any time. Should this be necessary, the sponsor or a specified designee will inform the appropriate regulatory authorities of the termination of the study and the reasons for its termination, and the principal investigator will inform the IRB/IEC of the same. If the decision is made to terminate the study, the sponsor and the principal investigator will assure that adequate consideration is given to the protection of the participants' interests.

The investigator may discontinue a participant from the study if warranted. The investigator and the sponsor may also request the withdrawal of a participant because of noncompliance (eg, missed visits), administrative reasons, or any other valid and ethical reasons.

Reasons for participant discontinuation may include, but are not limited to, the following:

- Investigator determination that it is not in the best interest of the participant to continue participation
- Intercurrent illness
- AE that is serious and unexpected
- Worsening condition
- Any other safety concerns

If a participant withdraws or is discontinued from the study before the Month-24 Visit, they should return for an exit visit. The schedule of assessments for this visit is the same as that for the 24 month.

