10.2 Visual Acuity

Participants with 15 or more letters of vision loss from baseline in the study eye will be tabulated and presented by treatment group. A 2-sample test of proportions will be performed to determine if there is a significant difference in proportions between the treatment groups through Month 24.

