10.3 Implant/Sham Site Examination

The number and percentage of study eyes with shifts deemed clinically significant in the implant surgical examination findings for the listed characteristics on the CRF from baseline to post-baseline will be tabulated by treatment group at each scheduled visit.

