10.5 Ophthalmic Examination

Ophthalmic examination findings with attention to the presence or absence of retinal findings or grading of disease eye will be listed for the study eye for individual participants. Intraocular pressure (IOP), and pupil size, change in intraocular pressure and change from baseline pupil size at each study visit will be summarized using mean, SD, median, minimum and maximum by treatment group. Number and percent of participants with an IOP of 21 mm Hg or greater and an increase of 5 mm Hg or more from Baseline at post-operative visits will be summarized.

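### The by-visit implant-site and intraocular-pressure tables have no place for findings measured only at unscheduled visits, and outside France no examination is scheduled between Week 1 and Month 6

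*SAP*

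**What the plan says.** **The general rule.** SAP 7.1: "Unscheduled measurements will be recorded as such and not attributed to a scheduled measurement time point, unless otherwise specified". Nothing in SAP section 10 mentions unscheduled measurements.

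**The tables.**
- SAP 10.3 counts clinically significant shifts at the implant or sham site "from baseline to post-baseline will be tabulated by treatment group at each scheduled visit".
- SAP 10.5 says of IOP and pupil size: "change in intraocular pressure and change from baseline pupil size at each study visit will be summarized". The same section adds a threshold count, IOP of 21 mm Hg or greater and "an increase of 5 mm Hg or more from Baseline at post-operative visits will be summarized".
- SAP 10.2 tabulates loss of 15 or more letters and tests for a "significant difference in proportions between the treatment groups through Month 24". SAP 3.2.2.2 lists this as a secondary safety endpoint.

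**The schedule.** After Day 1 and Week 1, Protocol 7.2.5 says of Month 1: "In regions other than France, telephone contact will be made with the participant to determine the following". The items are AEs and concomitant medications only. Protocol 7.2.6 says the same for Month 3. The next clinic examination outside France is Month 6 (Protocol 7.2.7).

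**Early exit.** Protocol 18: "If a participant withdraws or is discontinued from the study before the Month-24 Visit, they should return for an exit visit". That visit carries the Month 24 assessments. Neither SAP section 10 nor the schedule in SAP Appendix A gives it a time point.

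**The concern.** The site and IOP tables are the planned summary of local safety after intraocular surgery. Outside France, a measured site or pressure finding in the months after Week 1 can come only from an unscheduled examination. The by-visit tables have no row for such a value.

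The period matters clinically on the protocol's own account. Protocol 1.1 says: "Trace to mild inflammation is seen postoperatively in a minority of participants and typically clears by 3 months". SAP Appendix C lists vitreous inflammation, intraocular haemorrhage, scleral leak, device extrusion and high or low pressure among the site shifts. All of these could come and go, or reach their worst, between Week 1 and Month 6.

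Any loss is unlikely to be even between arms. Protocol 13 describes the sham as a superficial conjunctival procedure, so transient intraocular findings are expected mainly with the implant.

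For the 15-letter and IOP-threshold counts the problem is ambiguity. Two programmers could both follow the SAP and reach different counts, one of them for a secondary safety endpoint with a between-arm test. The last examination of a participant who withdraws early is in the same position.

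**Working it through.** The plan gives no figure on this point to reproduce. The check is visit-day arithmetic, a reading of each table, and an illustration under stated assumptions.

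**1. Length of the gap** (1 month = 30 days, Protocol 4.1; windows from Protocol 7.2)
- Week 1: Day 7 ± 2, so Days 5 to 9. Month 6: Day 180 ± 30, so Days 150 to 210.
- Outside France: nominal 180 − 7 = 173 days; shortest 150 − 9 = 141; longest 210 − 5 = 205.
- In France, with clinic visits at Day 30 ± 7 and Day 90 ± 14, the longest nominal interval in this period is Month 3 to Month 6: 180 − 90 = 90 days (46 to 134 with windows).

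**2. Is an unscheduled value included?**

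| Output | Basis in the SAP | Unscheduled value |
|---|---|---|
| Site shifts (10.3) | each scheduled visit | left out |
| IOP and pupil size (10.5) | each study visit | no row, given 7.1 |
| IOP threshold (10.5) | post-operative visits | not stated |
| 15-letter loss (10.2) | through Month 24 | not stated |
| AE tables (10.1) | all AEs after surgery | included if reported as an AE |

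Section 10 defines the Month 24 safety analysis as a period from surgery to that visit. This favours inclusion for the two cumulative counts but does not settle it.

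**3. What the schedule alone can catch** (illustration)

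*Assumption A:* onset uniform over Days 7 to 180, visits on nominal days, duration D. The share that starts and resolves between scheduled examinations is Σ max(0, gap − D)/173. The gap is 173 outside France; in France the gaps are 23, 60 and 90.
- D = 14: 159/173 = 92% outside France; (9 + 46 + 76)/173 = 76% in France.
- D = 30: 143/173 = 83%; (0 + 30 + 60)/173 = 52%. So 17% and 48% are caught.
- D = 60: 113/173 = 65%; 30/173 = 17%.
- D = 90: 83/173 = 48%; 0%.

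*Assumption B:* onset uniform over Days 8 to 150 (142 days), visit days uniform within their windows, D = 30.
- Month 6 catches on average (30²/2)/60 = 7.5 onset-days. Outside France: 7.5/142 = 5% (Week 1 adds less than 0.1 point).
- In France, Month 1 adds on average 30 − 8 = 22 onset-days and Month 3 adds 30: (22 + 30 + 7.5)/142 = 42%.

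The levels depend on the onset assumption (5% or 17% outside France, 42% or 48% in France). The ordering does not. These shares describe the visit schedule. Converting them into values dropped by the SAP rule would need the rate of unscheduled examinations, which the documents do not give.

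**The case against.** **Not attributing a value to a visit is not the same as excluding it.** SAP 7.1 bars relabelling an unscheduled value as, say, Month 6. A reader might infer that it also removes such values from the 15-letter and IOP-threshold counts. The text does not say so: both counts are cumulative, and section 10 defines safety by period. This objection stands. For those counts the SAP is open.

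**Harm seen between visits has another route.** A reader might infer that it would appear only in listings. Protocol 10 defines an AE as any untoward occurrence, and Protocol 10.2 allows mild events with no therapy. Protocol 10.3 names vitreous inflammation as a device-related example. AEs are asked about on both calls, and SAP 10.1 tabulates them all. This also stands. What can be lost is the measured value, or a finding that the site did not judge to be an AE. AE reporting does not fully replace examination data, because the ophthalmologist is unmasked (Protocol 5.6).

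**Day 1 and Week 1 are examined everywhere.** Inflammation present from surgery can be seen then. If onset is uniform over Days 0 to 7 and the Week 1 visit uniform over Days 5 to 9, Week 1 misses an onset only when it falls after the visit: 1/2 × 1/7 = 7%. So about 93% of findings lasting 9 days or more are caught. The gap therefore concerns findings that start, or peak, after Week 1.

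**The exit visit is never called unscheduled.** That is correct. The point is only that the SAP assigns it no place.

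**Scheduled-only tables are a defensible choice.** They keep ascertainment equal between arms, whereas unmasked sites may recall implanted participants more often. This is a reason to show both counts. It does not justify omitting the wider one.

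**Conclusion.** The point holds for the site-shift table and the by-visit IOP table. Outside France, a finding that starts and resolves within the gap of at least 141 days and is measured only at an unscheduled visit is missing from both, and reaches a summary table only as a reported AE. For the IOP table this rests on reading each study visit as each visit in the schedule. For the 15-letter loss, the IOP-threshold count and the early-exit visit, the SAP is incomplete but does not exclude the values.

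The documents do not support a claim that early surgical harm goes unreported or that the secondary vision endpoint is understated. The percentages above illustrate the schedule under assumed onset and duration, and do not measure the effect of the SAP rule. That effect depends on an unknown number of unscheduled examinations. The severity is minor to moderate: an inexpensive improvement to make before database lock.

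**What to change.** 1. In SAP 10.3 and 10.5, add a worst study-eye value summary for site findings and for IOP over all examinations from surgery through Month 24: scheduled, unscheduled and early exit.
2. In SAP 10.2 and 10.5, state that the 15-letter and IOP-threshold counts use that same set of examinations.
3. Show the scheduled-visit-only count beside each, so that extra looking by unmasked sites is visible.
4. Leave the by-visit means, and the SAP 7.1 rule for them, unchanged.

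The cost is a few lines of SAP text and a little programming on data already collected, with no change to visits or procedures. The one downside is that counts over all examinations may partly reflect more frequent recall of implanted participants. Item 3 shows this to the reader but does not remove it.
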